### **13.2.1 End of Study Visit**

Patients will report to the study site at the end of the study and have the assessments and procedures listed below completed. This visit may be incorporated at the scheduled 3-or 6-month visit.

- Assessment of AEs/SAEs;
- Complete physical exam with weight;
- Vital signs (seated position), including SBP, DBP, heart rate, respiration, and body temperature;
- 12-Lead ECG;
- Clinical laboratory tests;
- Urine pregnancy test in females of childbearing potential only;
- Concomitant medications;
- IP accountability;
- QoL

## **14 DATA QUALITY ASSURANCE**

Catalyst personnel or designees will visit or telephone the study site before initiation of the study to review with the site personnel information about the IP, protocol and other regulatory document requirements, source document requirements, CRFs, monitoring requirements, and procedures for reporting AEs/SAEs.

At visits during and after the study, a CRA will monitor the site for compliance with regulatory documentation, with a focus on accurate and complete recording of data on CRFs from source documents, adherence to protocol, AE/SAE reporting, and drug accountability records.

	SMA-002	Page 38
---	---------	---------

## 15 STATISTICAL METHODS AND DETERMINATION OF SAMPLE SIZE

### 15.1 Statistical and Analytical Plans

#### 15.1.1 Interim Analyses

No interim analyses are planned.

### 15.2 Analysis Populations

The analysis population in this study is the safety population and will consist of all patients who are enrolled in the Long-Term study and have received at least one dose of amifampridine.

### 15.3 Primary Endpoint

The primary endpoint of the study is safety and tolerability of amifampridine at Months 3, 6, 9, 12, 15, 21 and 27. For more details see Section [15.5](#) below.

### 15.4 Secondary Endpoint

The secondary endpoint of the study is the QoL scores at Months 3, 6, 9, 12, 15, 21 and 27.

### 15.5 Safety Analysis

Prior to analysis, all AEs will be coded using the MedDRA coding dictionary. Based on these coded terms, TEAEs and SAEs will be summarized using system organ class and preferred terms, as well as by relationship to treatment. All AEs will be listed, regardless of whether they were study treatment related.

Vital signs will be summarized using descriptive statistics (mean, standard deviation, median, minimum, maximum, and number of non-missing observations) by time point. Changes from baseline will also be summarized by post-dose time point.

Clinical laboratory parameters will be summarized using descriptive statistics (mean, standard deviation, median, minimum, maximum, and number of non-missing observations) by time point. Changes from baseline will also be summarized by post-dose time point. In addition, a shift table will be constructed to show the shifts in laboratory results by parameter relative to the normal ranges. The number and percentage of subjects with the following shifts will be presented: normal/normal, normal/low, normal/high, low/low, low/normal, low/high, high/low, high/normal, and high/high. Similar shift tables will also be constructed for physical exam results. ECG results will be summarized in a shift table with the following

	SMA-002	Page 39
---	---------	---------

shifts presented: normal/normal, normal/abnormal, abnormal/normal and abnormal/abnormal. A table of descriptive statistics for QTc will be created.

Additional safety analyses may be performed as described in the Statistical Analysis Plan (SAP) for the study.

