10.6 Final Analysis

All final, planned analyses identified in this SAP will be performed by SPARC Consulting, Milan, Italy on behalf of Catalyst Pharmaceuticals following Sponsor Authorization of this Statistical Analysis Plan, Database Lock, and Sponsor Authorization of Analysis Sets.

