10.12.2 Vital Signs and Body Weight

Analysis will be performed in the SAF analysis set.

Vital signs, including sitting blood pressure (systolic and diastolic; mmHg), sitting heart rate (beats/minute), body temperature (°C), respiration rate (breaths/minute), and weight (kg) will be summarized by time point using descriptive statistics. Changes from baseline will also be summarized by post-dose time point.

Height is recorded at Screening visit only.

BMI will be calculated at Screening visit according to the following formula:

$$BMI (kg/m^2) = ((body\ weight\ (kg))/(height\ (m))^2).$$

Height and BMI will be summarized using descriptive statistics.

10.12.3 12-Lead ECG

Analysis will be performed in the SAF analysis set.

A standard 12-lead ECG will be recorded at Screening, Months 3, 6, 9, 12, 15, 21 and 27 visit.

Each tracing will be classified as “Normal tracing”, “Abnormal tracing (not clinically significant)”, “Abnormal tracing (clinically significant)”, or “Unknown”.

ECG results will be summarized in a shift table with the following shifts presented (baseline versus post dose time point): normal/normal, normal/abnormal NCS, normal/abnormal CS, abnormal NCS/normal, abnormal NCS/abnormal NCS, abnormal NCS/abnormal CS, abnormal CS/normal, abnormal CS/abnormal NCS and abnormal CS/abnormal CS.

Clinically significant changes from baseline will be recorded as AEs.

Abnormalities reported will be coded using MedDRA thesaurus version 23.0, and the terms listed for all enrolled patients.

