13.1 Table Specifications

Tables will be provided as defined by the table shells.

All output will be generated by means of SAS System and exported into a Microsoft Word document in RTF format. All output will be in landscape orientation. Left and right margins will be 2 cm from the side; the top and bottom margins will be 2.5 cm. Font size will be Courier New 7 pt.

The header containing the sponsor name (Catalyst Pharmaceuticals) and protocol number will appear on the top left corner of each page of the output. The page number, in the format of “Page x of y”, will appear on the top right corner of the output, where y = last page of corresponding output.

Column headers in tables include the total possible numbers to be included in summaries for that table, designated as “(N=XX)”.

The SAS program name, the date of the creation of the output (run date) and the listings from which the tables were derived will appear on the bottom left corner as follows:

Source: [program name].sas, Run on ddmmmyyyy

Source: Listing(s) xx.x.x, xx.x.x

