Table 14.5.2. 12-Lead ECG / SAF

Statistic	Amifampridine (N=XX)
Screening	xx (x.x)
Normal tracing	n (%) xx (x.x)
Abnormal tracing, NCS	n (%) xx (x.x)
Abnormal tracing, CS	n (%) xx (x.x)
Unknown	n (%) xx (x.x)
Month 3	xx (x.x)
Normal tracing	n (%) xx (x.x)
Abnormal tracing, NCS	n (%) xx (x.x)
Abnormal tracing, CS	n (%) xx (x.x)
Unknown	n (%) xx (x.x)
...	
EOS	xx (x.x)
Normal tracing	n (%) xx (x.x)
Abnormal tracing, NCS	n (%) xx (x.x)
Abnormal tracing, CS	n (%) xx (x.x)
Unknown	n (%) xx (x.x)

CS: Clinically Significant.

NCS: Not Clinically Significant.

Source: xxx.sas, Run on ddmmmyyyy

Reference Listings: [16.2.7.3.](#)

Table 14.5.3. Childbearing Potential and Pregnancy Test / SAF

Visit		Amifampridine	
		Statistic	(N=xx)
Screening	Childbearing potential		
	Patient male	n (%)	xx (xx.x%)
	Menopause	n (%)	xx (xx.x%)
	Sterilized	n (%)	xx (xx.x%)
	Total hysterectomy	n (%)	xx (xx.x%)
	No contraception protection	n (%)	xx (xx.x%)
	Contraception protection	n (%)	xx (xx.x%)
	Child	n (%)	xx (xx.x%)
	Unknown	n (%)	xx (xx.x%)
	Pregnancy test performed?		
	No	n (%)	xx (xx.x%)
	Yes	n (%)	xx (xx.x%)
	Not applicable	n (%)	xx (xx.x%)
	Type of pregnancy test (#)		
	Urine dipstick	n (%)	xx (xx.x%)
	Serum	n (%)	xx (xx.x%)
	Unknown	n (%)	xx (xx.x%)
	Pregnancy test result (#)		
	Negative	n (%)	xx (xx.x%)
	Positive	n (%)	xx (xx.x%)
	Unknown	n (%)	xx (xx.x%)

Percentages are calculated on the number of patients (N) in the SAF analysis set.

Percentages are based on the number of female patients performing pregnancy test.

Source: xxx.sas, Run on ddmmmyyyy

Reference Listings: [16.2.7.1.](#)

Programming Notes: To be repeated for Month 3, Month 6, Month 9, Month 12, Month 15, Month 21, Month 27 and EOS visits.

Table 14.6.1. Summary of INQoL: Weakness / ITT_{QoL}

Visit	Actual Values					Change from Screening						
	n	Mean	SD	Min	Median	Max	n	Mean	SD	Min	Median	Max
Screening	xx	xx.x	xx.x	xx.x	xx.x	xx.x						
Month 3	xx	xx.x	xx.x	xx.x	xx.x	xx.x	xx	xx.x	xx.x	xx.x	xx.x	xx.x
Month 6	xx	xx.x	xx.x	xx.x	xx.x	xx.x	xx	xx.x	xx.x	xx.x	xx.x	xx.x
Month 9	xx	xx.x	xx.x	xx.x	xx.x	xx.x	xx	xx.x	xx.x	xx.x	xx.x	xx.x
Month 12	xx	xx.x	xx.x	xx.x	xx.x	xx.x	xx	xx.x	xx.x	xx.x	xx.x	xx.x
Month 15	xx	xx.x	xx.x	xx.x	xx.x	xx.x	xx	xx.x	xx.x	xx.x	xx.x	xx.x
Month 21	xx	xx.x	xx.x	xx.x	xx.x	xx.x	xx	xx.x	xx.x	xx.x	xx.x	xx.x
Month 27	xx	xx.x	xx.x	xx.x	xx.x	xx.x	xx	xx.x	xx.x	xx.x	xx.x	xx.x
EOS	xx	xx.x	xx.x	xx.x	xx.x	xx.x	xx	xx.x	xx.x	xx.x	xx.x	xx.x

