- 4 Concomitant use with medicinal products with a narrow therapeutic window.
- 5 Concomitant use with medicinal products with a known to cause QTc prolongation.
- 6 Clinically significant abnormalities in 12 lead ECG, in the opinion of the Investigator.
- 7 Subjects with congenital QT syndromes.
- 8 Breastfeeding or pregnant at Screening or planning to become pregnant at any time during the study.
- 9 Intolerable amifampridine-related side effects
- 10 Treatment with an investigational drug (other than amifampridine) or device while participating in this study.
- 11 Any medical condition that, in the opinion of the Investigator, might interfere with the patient's participation in the study, poses an added risk for the patient, or confound the assessment of the patient.
- 12 History of drug allergy to any pyridine-containing substances or any amifampridine excipient(s).

[According to Study Protocol version 3.0]

- 1 Epilepsy and currently on medication.
- 2 Uncontrolled asthma.
- 3 Concomitant use with sultopride.
- 4 Concomitant use with medicinal products with a narrow therapeutic window.
- 5 Clinically significant abnormalities in 12 lead ECG, in the opinion of the Investigator.
- 6 Breastfeeding or pregnant at Screening or planning to become pregnant at any time during the study.
- 7 Intolerable amifampridine-related side effects
- 8 Treatment with an investigational drug (other than amifampridine) or device while participating in this study.
- 9 Any medical condition that, in the opinion of the Investigator, might interfere with the patient's participation in the study, poses an added risk for the patient, or confound the assessment of the patient.
- 10 History of drug allergy to any pyridine-containing substances or any amifampridine excipient(s).

Listing 16.2.2.2. Exclusion Criteria

Site	Patient	Date of visit	Consent date	Protocol version	Criterion (1)											
					1.	2.	3.	4.	5.	6.	7.	8.	9.	10.	11.	12.
xxx	xxx	DDMMYYYY	DDMMYYYY	xxx	xxx	xxx	xxx	xxx	xxx	xxx	xxx	xxx	xxx	xxx	xxx	xx
xxx	xxx	DDMMYYYY	DDMMYYYY	xxx	xxx	xxx	xxx	xxx	xxx	xxx	xxx	xxx	xxx	xxx	xxx	xx
xxx	xxx	DDMMYYYY	DDMMYYYY	xxx	xxx	xxx	xxx	xxx	xxx	xxx	xxx	xxx	xxx	xxx	xxx	xx
xxx	xxx	DDMMYYYY	DDMMYYYY	xxx	xxx	xxx	xxx	xxx	xxx	xxx	xxx	xxx	xxx	xxx	xxx	xx

See first page for criteria.

(1) Response for each criterion: Yes, No, Not Applicable

Source: [program name].sas, Run on ddmmmyyyy.

Programming Note: Sort by site and patient number. Place the criteria on the first page.

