Site	Patient	Visit	Were vital signs collected?	Date of examination	Sitting SBP (mmHg)		Sitting DBP (mmHg)		Sitting heart rate (bpm)		Respiration rate (breaths/min)		Body temperature (°C)		Body weight (kg)	
					Value	CFB	Value	CFB	Value	CFB	Value	CFB	Value	CFB	Value	CFB
xxx	xxx	Screening	xxx	DDMMYYYY	xxx		xxx		xxx		xxx		xxx		xxx	
		Month 3	xxx	DDMMYYYY	xxx	xxx	xxx	xxx	xxx	xxx	xxx	xxx	xxx	xxx	xxx	xxx
		Month 6	xxx	DDMMYYYY	xxx	xxx	xxx	xxx	xxx	xxx	xxx	xxx	xxx	xxx	xxx	xxx
		Month 9	xxx	DDMMYYYY	xxx	xxx	xxx	xxx	xxx	xxx	xxx	xxx	xxx	xxx	xxx	xxx
		Month 12	xxx	DDMMYYYY	xxx	xxx	xxx	xxx	xxx	xxx	xxx	xxx	xxx	xxx	xxx	xxx
		...	xxx	DDMMYYYY	xxx	xxx	xxx	xxx	xxx	xxx	xxx	xxx	xxx	xxx	xxx	xxx
		EOS	xxx	DDMMYYYY	xxx	xxx	xxx	xxx	xxx	xxx	xxx	xxx	xxx	xxx	xxx	xxx
xxx	xxx	Screening	xxx	DDMMYYYY	xxx		xxx		xxx		xxx		xxx		xxx	
		Month 3	xxx	DDMMYYYY	xxx	xxx	xxx	xxx	xxx	xxx	xxx	xxx	xxx	xxx	xxx	xxx
		Month 6	xxx	DDMMYYYY	xxx	xxx	xxx	xxx	xxx	xxx	xxx	xxx	xxx	xxx	xxx	xxx
		Month 9	xxx	DDMMYYYY	xxx	xxx	xxx	xxx	xxx	xxx	xxx	xxx	xxx	xxx	xxx	xxx
		Month 12	xxx	DDMMYYYY	xxx	xxx	xxx	xxx	xxx	xxx	xxx	xxx	xxx	xxx	xxx	xxx
		...	xxx	DDMMYYYY	xxx	xxx	xxx	xxx	xxx	xxx	xxx	xxx	xxx	xxx	xxx	xxx
		EOS	xxx	DDMMYYYY	xxx	xxx	xxx	xxx	xxx	xxx	xxx	xxx	xxx	xxx	xxx	xxx

CFB=Change from Baseline.

Source: [program name].sas, Run on ddmmmyyyy.

Programming Notes: Sort by site, patient number and visit. Height is recorded with Demography at Screening only.

Listing 16.2.7.3. ECG

Site	Patient	Visit	Was an ECG performed?	Date performed	Tracing (1)	If Abnormal, please specify	System Organ Class	Preferred Term
xxx	xxx	Screening	xxx	DDMMYYYY	xxxxxxxxxx			
		Month 3	xxx	DDMMYYYY	Abnormal	XXXXXXXX	xxxxxxxxxx	xxxxxxxxxx
		...	No					
		EOS	xxx	DDMMYYYY	xxxxxxxxxx			
xxx	xxx	Screening	xxx	DDMMYYYY	xxxxxxxxxx			
		Month 3	xxx	DDMMYYYY	Abnormal	XXXXXXXX	xxxxxxxxxx	xxxxxxxxxx
		...	xxx	DDMMYYYY	xxxxxxxxxx			
		EOS	xxx	DDMMYYYY	xxxxxxxxxx			

(1) Tracing Assessment: Normal tracing, Abnormal tracing (not clinically significant), Abnormal tracing (clinically significant), UNK.

Source: [program name].sas, Run on ddmmmyyyy.

Programming Note: Sort by site, patient number and visit.

Listing 16.2.7.4. Physical Examination

(1) Was a complete physical examination performed?

(2) Result: Normal, Abnormal, Not examined

Source: [program name].sas, Run on ddmmmyyyy.

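### The SAP omits the QTc table and the physical-examination shift tables promised in Protocol 15.5, while its Section 12 declares no change

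*Protocol*

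**What the plan says.** Protocol 15.3 refers to Protocol 15.5 for the detail of the primary endpoint, which is safety and tolerability. For ECGs, Protocol 15.5 promises a normal/abnormal shift table and a separate numeric summary: "A table of descriptive statistics for QTc will be created". For physical examination it promises shift tables similar to the laboratory ones.

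SAP 10.12.3 sets the schedule ("A standard 12-lead ECG will be recorded at Screening, Months 3, 6, 9, 12, 15, 21 and 27 visit") and sorts each tracing into normal, abnormal not clinically significant, abnormal clinically significant, or unknown. The one summary it plans is described as follows: "ECG results will be summarized in a shift table with the following shifts presented (baseline versus post dose time point", after which it names nine pairs of categories. The only ECG shell, "Table 14.5.2. 12-Lead ECG / SAF", counts those categories visit by visit. ECG Listing 16.2.7.3 carries the same classification ("Tracing Assessment: Normal tracing, Abnormal tracing (not clinically significant), Abnormal tracing (clinically significant), UNK") with a free-text description of any abnormality and its coded term.

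SAP 10.12.4 and shell 14.1.12 summarize physical examination as counts and percentages at each visit. SAP Section 12 states that the SAP brings in no change to the protocol's analyses. On scope, SAP 10.6 says "All final, planned analyses identified in this SAP will be performed" and SAP 13.1 says "Tables will be provided as defined by the table shells". Protocol 15.7 adds that where the two documents differ, the final SAP governs and no amendment follows.

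**The concern.** Two pre-specified safety outputs disappear between protocol and SAP, and the section meant to disclose such differences says there are none. A reader of the study report who relied on Section 12 would not know that the outputs had been planned.

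QTc is not an arbitrary variable here. Protocol 8.2 lists QTc prolongation among the clinically significant or serious events seen in more than one patient on this drug (2/1,454; 0.14%). A category of normal or abnormal cannot show a drift in the interval within tracings that are all read as normal, and a numeric table is the output that would.

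For physical examination, visit-by-visit counts cannot show who changed. The same number abnormal at baseline and at a later visit may be the same patients or entirely different ones.

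**Working it through.** No arithmetic decides this point, so the check sets the two documents side by side.

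1. **Which protocol the SAP follows.** SAP Section 4 says it takes version 3.0 of 12 April 2019 into account. Section 15.5 of that version contains both commitments, so the gap does not come from a superseded text.

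2. **Promised output against planned output.**

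| Protocol 15.5 | SAP text | SAP shell | SAP listing |
|---|---|---|---|
| QTc descriptive statistics | None in 10.12.3 | None | No QTc column in 16.2.7.3 |
| Physical-examination shift tables | By-visit counts in 10.12.4 | 14.1.12, by-visit counts | 16.2.7.4, result by visit |
| ECG shift table | Planned in 10.12.3, 3 x 3 = 9 pairs | None; 14.5.2 is a frequency table | 16.2.7.3, category by visit |

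3. **Where QTc occurs in the SAP text supplied.** It occurs once, in Listing 16.2.2.2, which reprints a version 2.0 exclusion criterion: "Concomitant use with medicinal products with a known to cause QTc prolongation". That is an eligibility item, not a measurement.

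4. **Whether a general sentence covers it.** SAP 10.2 says that summary statistics will be given for every safety and efficacy variable. That helps only if QTc is a variable in the SAP. SAP 9.2 names ECGs without any interval, and SAP 10.12.3 defines the ECG result by tracing category alone. There is no QTc variable for the sentence to act on.

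5. **Effect of running the SAP as written.** SAP 10.6 covers what the SAP identifies. QTc statistics and physical-examination shifts are identified nowhere, so neither is produced. The ECG shift table is identified in 10.12.3 and is still required. Its missing shell is an internal gap in the SAP and not a changed analysis.

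6. **Section 12 against rows one and two.** The protocol plans 1 QTc table and the SAP plans 0. The protocol plans physical-examination shift tables and the SAP plans 0. Either row alone makes the declaration incorrect.

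**The case against.** The best defence is that the protocol makes the SAP the governing text. That settles which document is followed. It does not make Section 12 accurate, and because no amendment will be issued, Section 12 is where the difference should be disclosed. Protocol 15.5 does allow the SAP to add safety analyses, but that permission does not extend to dropping one without saying so.

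A second defence concerns weight, and much of it stands. The protocol synopsis assesses safety by the incidence of treatment-emergent adverse events, with ECGs evaluated in addition. The study is uncontrolled, plans about 12 patients and tests no hypothesis (Protocol 15.6). Protocol 10.6.5 and SAP 10.12.3 both have clinically significant ECG changes recorded as adverse events, and reported abnormalities are coded and listed. Physical-examination results are listed by visit, so a reader could rebuild the shifts by hand.

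A reader might also infer more than the documents support:

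- That no QTc value can appear in any output. The free-text field in Listing 16.2.7.3 could carry one for a tracing read as abnormal.
- That QTc was never captured. Protocol 10.6.5 names no intervals, and no listing has a QTc field although SAP 10.2 says all collected data will be listed. But the eCRF is not supplied, and mock listings do not prove what was recorded.
- That the missing ECG shift shell is a third undeclared departure. The analysis itself is still planned in SAP 10.12.3.

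**Conclusion.** The point holds. The SAP omits the QTc table and the physical-examination shift tables that Protocol 15.5 commits to, and Section 12 is wrong to declare no change.

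The size is modest. What is certainly lost is systematic numeric QTc, chiefly within tracings read as normal. The physical-examination loss is one of presentation. The documents do not support reading this as a failure to detect or report clinically significant ECG changes.

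The conclusion rests on the SAP text supplied, from which some front matter was removed. It does not depend on whether QTc is in the database. If QTc is there, a promised table is being left out; if it is not, a promised table cannot be produced. Both need declaring if left as they are.

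**What to change.** SAP Section 4 provides for review, and revision if necessary, before final analyses. At that step:

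1. **QTc.** Establish whether the database holds QTc, or whether it can be transcribed from existing tracings. If so, add by-visit n, mean, SD, median, minimum and maximum to SAP 10.12.3, with a table shell and a column in Listing 16.2.7.3. State the correction formula, since neither document names one. If not, declare the omission and its reason in Section 12.
2. **Physical examination.** Restore the shift tables with a shell, or declare the change in Section 12.
3. **Section 12.** Correct the statement in every case. If both outputs are restored, make sure it is true of the revised SAP; otherwise list the departures.
4. **Separately,** add a shell for the nine-pair ECG shift table already planned in SAP 10.12.3. Shell 14.5.2 can stay as a frequency table.

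The cost is up to three shells (QTc, physical-examination shifts, ECG shifts), one listing column and a few lines of text. If QTc is not in the eCRF, add transcription and the source verification described in Protocol 17. No new visits or patient procedures are needed.

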### **15.6 Determination of Sample Size**

The study is not powered with respect to any endpoint and no hypothesis is being tested.

### **15.7 Changes in the Conduct of the Study or Planned Analyses**

Any change in study conduct considered necessary by the Investigator will be made only after consultation with Catalyst, who will then issue a formal protocol amendment to implement the change. The only exception is when an Investigator considers that a patient's safety is compromised without immediate action.

Protocol amendments that influence patient risk or the study objectives, or require revision of the ICF, must receive approval from the IEC prior to their implementation.

When a protocol amendment substantially alters the study design or the potential risks or burden to patients, the ICF will be amended and approved by Catalyst and the IRB/IEC/REB, and all active patients must again provide informed consent.

Note: If discrepancies exist between the text of the statistical analysis as planned in the protocol, and the final SAP, a protocol amendment will not be issued, and the SAP will prevail.

## **16 COMPENSATION, INSURANCE, AND INDEMNITY**

There will be no charge to study patients to be in this study. Catalyst will pay all costs of tests, procedures, and treatments that are part of this study (as included in the site budget). In addition, after IEC approval, Catalyst may reimburse the cost of travel for study-related visits. Catalyst will not pay for any hospitalizations, tests, or treatments for medical problems of any sort, whether or not related to the study patient's disease that are not part of this study. Costs associated with hospitalizations, tests, and treatments should be billed and collected in the way that such costs are usually billed and collected.

The Investigator should contact Catalyst immediately upon notification that a study patient has been injured by the IP or by procedures performed as part of the study. Any patient who experiences a study-related injury should be instructed by the Investigator to seek medical

	SMA-002	Page 40
---	---------	---------

treatment at a pre-specified medical institution if possible, or at the closest medical treatment facility if necessary. The patient should be given the name of a person to contact to seek further information about, and assistance with, treatment for study-related injuries. If the patient has followed the Investigator's instructions, Catalyst will pay for reasonable and necessary medical services to treat the injuries caused by the IP or study procedures, if these costs are not covered by health insurance or another third party that usually pays these costs.

